6.3 Demographic and Baseline Characteristics

Demographic and baseline characteristic data will include age (based on date of informed consent), age group (18-35 years, 36-55 years, 56-65 years), sex, race, ethnicity, height, and weight. Age will be calculated as an integer in years as the difference between the subject’s date of informed consent and the date of birth.

Demographic and baseline characteristic data will be summarized for all subjects in the ITT and Safety populations by treatment group and overall. Data will also be presented in a by-subject listing.

6.4 Medical History

Medical and psychiatric history will be collected at screening. All medical and psychiatric history terms will be coded by using Medical Dictionary for Regulatory Activities (MedDRA), version 24.0 – Mar 2021. A table will be generated to summarize medical history by system organ class (SOC) and preferred term (PT). Data will be summarized for all subjects in the Safety Population by treatment group and overall. A subject will be counted only once at each level of reporting. Data will also be presented in a by-subject listing, which will include system SOC, PT, and the verbatim term.

6.5 Reproductive System

Reproductive system information will be collected for applicable subjects during screening. The data will be provided in a by-subject listing.

6.7 Mini International Neuropsychiatric Interview (MINI)

The MINI will be completed during screening for all subjects. The data will be provided in a by-subject listing.

6.8 Prior and Concomitant Medication

Prior medications are those which have been identified to have been discontinued prior to the first dose of study medication. Concomitant medications are those which have been identified to have been taken at any point during the study after the first dose of study medication, including medications which started prior to first dose of study drug that are ongoing at first dose. The medications will be coded using B3 WHO Drug Global – Mar 2021.

Partial dates will be imputed according to Section 5.7 for the determination of prior, concomitant, and subsequent medications.

The incidence of prior and concomitant medications will be summarized by Anatomical Therapeutic Chemical (ATC) Level 2 classification and preferred term for all subjects in the Safety Population by treatment group and overall. Concomitant medications will be categorized according to whether they were taken before Visit 3 dosing, during or after Visit 3 dosing, or both. Medications categorized as “Before Visit 3 Dosing” will be those concomitant medications that were taken prior to dosing at Visit 3. Medications categorized as “During or After Visit 3 Dosing” will be those that were taken at any point after dosing at Visit 3. Medications that are ongoing or have an end date that matches the date of Visit 3 dosing will be categorized as “During or After Visit 3 Dosing”. A medication may be counted as both “Before Visit 3 Dosing” and “During or After Visit 3 Dosing” if taken during both time periods.

Finally, all prior and concomitant medication data will be presented in a by-subject listing. The listing will include ATC Level 2 classification, preferred term, and verbatim term.

6.9 Concomitant Therapies and Procedures

Concomitant therapies and procedures will be collected and coded using MedDRA v24.0 - Mar 2021. Concomitant therapies and procedures will be summarized similarly to concomitant medications and presented in a by-subject listing. The listing will include SOC, PT, and verbatim term and will indicate whether the therapy or procedure occurred before or after Visit 3 dosing.

6.10 Previous Psychotropic Drug Treatment

Previous psychotropic drug treatments taken more than one month prior to screening will be documented separately from prior and concomitant medications. These previous psychotropic

drugs will be coded and summarized using B3 WHO Drug Global – Mar 2021. The data will also be presented in a by-subject listing.

6.11 Previous Non-Drug Mental Health Treatment

Previous non-drug mental health treatments will be documented separately from concomitant therapies and procedures. These previous non-drug mental health treatments will be coded and summarized using MedDRA v24.0 - Mar 2021. The data will also be presented in a by-subject listing.

6.12 Investigational Product Exposure and Compliance

Site personnel will instruct the subject to self-administer the IP by one spray into each nostril (right and left nasal passages), for two total sprays per dose; thus, one dose equals 2 sprays, or 3.2 μ g.

All vials dispensed at Visit 2 will contain [REDACTED]

The total number of doses of placebo and PH94B will be summarized by treatment group.

Data will also be presented in a by-subject listing.

7 EFFICACY

All efficacy analysis reporting will be based on the ITT Population.

7.1 Primary Efficacy: Estimand, Endpoint and Analyses

7.1.1 Primary Estimand

Attribute	Definition
Treatment	The treatment of interest is PH94B, 3.2 µg administered as an intranasal (i.n.) solution (a 1.6 µg spray to each nostril per dose).
Population	The population of interest is adult subjects with SAD as defined by the protocol inclusion / exclusion criteria.
Endpoint	The endpoint to be measured is the change from baseline (Visit 2) to Visit 3 in average SUDS score during a 5-minute public speaking challenge.
Intercurrent Events (ICEs)	ICEs are expected to be rare. Any ICE that does occur will be handled using the treatment policy strategy, i.e., included in the treatment regimen under evaluation. See Section 5.6.
Population Summary	The difference of means from Visit 2 to Visit 3 in SUDS score will be estimated for each treatment group. PH94B will be compared to placebo using differences in group means.

7.1.2 Primary Endpoint and Analysis – Average SUDS Scores

The primary efficacy endpoint of the study is the difference in average SUDS score during a 5-minute public speaking challenge after treatment with PH94B or placebo at Visit 3 and the average SUDS score during a similar 5-minute public speaking challenge after treatment with placebo at Baseline (Visit 2).

The SUDS, used at Visit 2 and Visit 3 as part of each public speaking challenge, is scored 0–100. It is a standard instrument for rating social and performance anxiety in patients with SAD during role playing situations. Appendices A and B in the study protocol provide further detail on the public speaking challenge and SUDS scores.

An ANCOVA model will be used to test the null hypothesis that there is no difference in change from baseline average SUDS scores between PH94B- and placebo-treated subjects. Treatment group and analysis site will be included as factors and baseline average SUDS score as a covariate. [REDACTED]

[REDACTED]

[REDACTED]

[REDACTED]

It is expected that all subjects who are randomized at Visit 3 will complete the Visit 3 public speaking challenge immediately after randomization and be included in the primary efficacy analysis. [REDACTED]

[REDACTED]

The effects of the missing data will be evaluated through the results of the planned sensitivity analyses described in Section 6.2.1.3.

7.1.2.1 *Sensitivity Analyses*

Sensitivity analyses will be performed for the primary efficacy outcome. If imputation of missing data is required, a complete case sensitivity analysis will be implemented.

Additional sensitivity analyses may include imputation using treatment group mean SUDS change scores and imputation of zero change from baseline.

In order to satisfy requirements of a CAPA, an additional sensitivity analysis will be done by performing the primary analysis with Subjects 0101, 0103, and 0104 removed. If removal of these subjects results in an analysis site with too few patients for parameter estimation, then the model will be run without analysis site, both with and without the three subjects.

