3.4 RANDOMIZATION AND BLINDING

Overall, the randomization will be stratified by study site with a ratio of 1:1.

Each study site will be provided with a supply of blinded IP, each vial individually numbered with a unique alpha-numeric identification code. For Visit 2 and Visit 3, the interactive system will provide a unique vial identification code indicating the medication vial to be dispensed to the subject. The vial identification codes will be recorded in the drug dispensing record and the electronic case report form (eCRF).

The vial number can be used to break the blind if necessary. Contact information will be provided to the study site.

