8.2.2 Efficacy Analysis

8.2.2.1 Primary Endpoint

The primary endpoint for the Study is the difference in average SUDS scores during the [REDACTED] Visit 3 public speaking challenge versus the average SUDS scores during [REDACTED] Visit 2 public speaking challenge [REDACTED]

[REDACTED]
[REDACTED]
Change from Visit 2 to Visit 3 in average SUDS scores [REDACTED]

[REDACTED] will be used.

An ANCOVA model with baseline SUDS as covariate will be used to test the null hypothesis that there is no difference in change from baseline average SUDS scores between PH94B- and placebo-treated subjects.

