3.3 Randomization and Blinding

Randomization will be stratified within study site with a ratio of 1:1.

[figure not shown]
Each study site will be provided with a supply of blinded IP, each vial individually numbered with a unique alpha-numeric identification code. For Visit 2 and Visit 3, the interactive system

will provide a unique vial identification code indicating the medication vial to be dispensed to the subject. The vial identification codes will be recorded in the drug dispensing record and the electronic case report form (eCRF).

The vial number can be used to break the blind if deemed medically necessary by the medical monitor. Contact information will be provided to the study site.

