5 GENERAL CONSIDERATIONS

5.1 General Data Handling

All analyses will be conducted based on SAS 9.4 or higher.

In general, analysis tables will be presented by Visit 3 treatment group using the following groupings of subjects:

- PH94B
- Placebo
- Overall

Data will be presented in by-subject data listings. Subject ID will be four digits consisting of the site ID (first two digits) and subject number (last two digits). Unless otherwise stated, all listings will be sorted by treatment group, subject ID, and assessment date (and time, if available).

Unless stated otherwise, continuous data will be summarized by Visit 3 treatment group based on n, mean, median, standard deviation (SD), minimum value, and maximum value.

Unless stated otherwise, categorical data will be summarized by Visit 3 treatment group using n and percentage based on the number of non-missing values.

The precision level used for descriptive statistics will be based on the following:

- Minimum and Maximum: same number of significant digits as the raw data.
- Mean, Median, Q1, and Q3 (as applicable): one additional decimal place to that reported for Minimum and Maximum
- SD: two additional decimal places than the Minimum and Maximum
- Percentages <100% will be reported to one decimal place and percentages of 100% will be reported with no decimal place.
- P-values will be reported to four decimal places. If the value is below 0.0001 it will be noted as < 0.0001; if the value above 0.9999 it will be noted as > 0.9999.

Unless otherwise noted, statistical inference will be based on a 5% significance level (i.e., 95% confidence intervals will be produced).

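### If site 01 becomes too small, the CAPA sensitivity analysis drops site for the whole trial, so it answers its question on a model other than the primary ANCOVA, with no estimability need

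*SAP*

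**What the plan says.** SAP 7.1.2 defines the primary ANCOVA on change in average SUDS: "Treatment group and analysis site will be included as factors and baseline average SUDS score as a covariate". Text directly after this statement is redacted, and the visible text does not define analysis site.

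Under Sensitivity Analyses (SAP 7.1.2.1), the CAPA item consists of "performing the primary analysis with Subjects 0101, 0103, and 0104 removed". A conditional fallback follows. Its trigger is that a site is left too small for its parameters to be estimated, and its action is "then the model will be run without analysis site, both with and without the three subjects". The visible text gives no number for what counts as too few.

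SAP 5.1 makes the first two digits of the subject ID the site number, and Protocol 5.2.1 also has subject numbers begin with the site number. All three subjects are therefore from site 01.

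On allocation, SAP 3.3 says "Randomization will be stratified within study site with a ratio of 1:1", and Protocol 3.4 agrees: "Overall, the randomization will be stratified by study site with a ratio of 1:1".

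**The concern.** The CAPA question is whether three subjects at one site drive the primary result. The natural answer is the primary model refitted without them. If the fallback is triggered, neither of its two runs is that model: a shortage at site 01 removes the site factor for every site, up to about 18 by the protocol synopsis.

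When allocation is balanced within sites and sites differ, leaving site out of the model puts between-site variation into the residual, and the reported standard error becomes too large. A sound primary result could then look weaker in this analysis for a reason unrelated to the three subjects. The no-site run with all subjects included also need not match the reported primary result.

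**Working it through.** **Plan's own figure.** The plan gives no figure for this point. The total of 208 subjects (104 per arm) cannot be reproduced because its inputs are redacted, and it is not in dispute.

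**Inputs.** From the documents: 208 subjects, up to about 18 sites (208/18 = 11.6 per site), 5% significance level, and Phase 2 improvements of 26.7 and 14.0 points with n = 45 and 46 and t = 3.16 (Protocol 1.2.2). These imply an SD of change of

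12.7 / (3.16 × √(1/45 + 1/46)) = 19.2.

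Assumed, because the documents do not give them: between-site ICC of 0 to 0.20, blocks of 4 within site, the number randomized at site 01, and (for power only) a true effect of 8.7 points.

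**Step 1: is the fallback needed?** With 18 sites the visible model has 1 intercept + 1 treatment + 1 baseline + 17 site terms = 20 columns.

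- All subjects: 208 − 20 = 188 residual df.
- Three removed, one left at site 01: full rank (20 of 20), 205 − 20 = 185 df.
- Three removed, none left: the site 01 term disappears, full rank (19 of 19), 205 − 19 = 186 df.
- Site dropped altogether: 3 columns, 205 − 3 = 202 df.

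The treatment effect is estimable in every case. A lone remaining subject is fitted exactly by its own site term and adds nothing to the treatment contrast; no other site is affected.

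**Step 2: standard error by hand.** Without site, SE ≈ 19.2 × √(2/104) = 2.66. With site, the residual variance shrinks by the factor (1 − ICC), so the ratio of no-site to site-adjusted SE is about 1/√(1 − ICC): 1.00, 1.03, 1.05 and 1.12 at ICC 0, 0.05, 0.10 and 0.20.

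**Step 3: simulation.** 3,000 trials per setting. The table has five subjects randomized at site 01, so two are left after removal. Entries are mean SEs of the treatment effect.

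| ICC | Primary, all subjects | Site kept, three removed | Site 01 merged, three removed | No site, all subjects | No site, three removed |
|---|---|---|---|---|---|
| 0 | 2.661 | 2.685 | 2.679 | 2.658 | 2.678 |
| 0.05 | 2.594 | 2.618 | 2.613 | 2.657 | 2.676 |
| 0.10 | 2.527 | 2.550 | 2.547 | 2.654 | 2.673 |
| 0.20 | 2.383 | 2.405 | 2.405 | 2.650 | 2.669 |

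- Same subjects, no site against site kept: 2.678/2.685 = 1.00, 2.676/2.618 = 1.02, 2.673/2.550 = 1.05, 2.669/2.405 = 1.11.
- No site with three removed, against the primary: 1.01, 1.03, 1.06, 1.12.
- Merged with three removed, against the primary: 1.01 in every row.

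With four subjects at site 01 (one left), the site-kept and no-site SEs after removal are 2.549 and 2.672 at ICC 0.10, and 2.405 and 2.664 at ICC 0.20. These are the same ratios, 1.05 and 1.11.

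**Step 4: what the larger SE means.** The no-site estimate is not itself noisier. At ICC 0.10 in the table's setting, its empirical SD after removal is 2.570, against 2.569 with site kept; the reported SE of 2.673 overstates it. Type I error after removal, no site against site kept, is 0.044 v 0.044 (ICC 0), 0.047 v 0.052 (0.05), 0.041 v 0.050 (0.10) and 0.033 v 0.051 (0.20), with a simulation error of about √(0.05 × 0.95/3000) = 0.004. Power at 8.7 points is 0.905 v 0.919 at ICC 0.10 and 0.918 v 0.946 at ICC 0.20. In a separate simulation with about 12 subjects per site and ICC 0.05 to 0.20, the models with and without site disagreed at the 5% level in 0.7% to 3.5% of trials.

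**The case against.** The strongest reply is that the fallback is already paired. A reader might infer that a changed result could not be attributed either to the three subjects or to the loss of site. The documents do not support that. The primary fit against the no-site fit with all subjects isolates the loss of site, and the two no-site fits isolate the three subjects (mean SE 2.654 against 2.673 at ICC 0.10). This stands. What remains is that the second comparison is made on a model the trial does not rely on.

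Other replies also carry weight:

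- Read literally, the trigger may never be met, because the treatment effect is always estimable in the visible model. The default, which keeps site, would then apply. That makes the fallback either idle or, under a stricter reading of too few, a switch to another model.
- One might call a pooling rule missing, or equate analysis site with the stratification factor. Neither can be shown: a definition or grouping rule may lie in the redacted text.
- Merging site 01 also alters the site factor. It is like for like only if the merged model is run with and without the three subjects. It does stay within about 1% of the primary SE.
- The visible protocol model (8.2.2.1) is "An ANCOVA model with baseline SUDS as covariate will be used to test the null hypothesis" and does not name site, so the no-site run matches it. But the CAPA item refers to the primary analysis, which the SAP specifies with site.
- The analysis is conditional and supportive. SAP 5.7 describes formal testing only of the primary and then the secondary endpoint.

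**Conclusion.** The point holds as a minor one. If triggered, the fallback answers the CAPA question on a model without site instead of the SAP's primary ANCOVA, although randomization is stratified by study site, and estimability does not require it. The standard error is essentially unchanged at ICC 0, about 5% too large at ICC 0.10, and 11% (same subjects) to 12% (against the primary) too large at ICC 0.20. The test becomes conservative, with type I error near 3% at ICC 0.20.

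These sizes rest on the assumed ICCs, 18 sites, an SD of 19.2 and blocks of 4. The estimability argument rests on the visible main-effects model; if redacted text adds terms such as a treatment-by-site interaction, it would need rechecking. It would be wrong to infer that the primary test or its type I error is at risk: both are unaffected.

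**What to change.** Replace the fallback in SAP 7.1.2.1 with:

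*Analysis site will be retained in the model; if needed, the affected site will be merged using the analysis-site grouping rule of the primary model, fixed before unblinding, and that model will be run both with and without the three subjects.*

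Also state the site size that counts as too few. The number left at site 01 can be counted without treatment codes, so this can be settled while blinded.

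The cost is one SAP sentence and a merging partner for site 01 named in advance. If a grouping rule already stands in the redacted text, a cross-reference to it is enough.

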7.2 Secondary Efficacy: Estimand, Endpoint and Analysis

7.2.1 Secondary Estimand

Attribute	Definition
Treatment	The treatment of interest is PH94B, 3.2 µg administered as an intranasal (i.n.) solution (a 1.6 µg spray to each nostril per dose).
Population	The population of interest is adult subjects with SAD as defined by the protocol inclusion / exclusion criteria.
Endpoint	The endpoint to be measured is the CGI-I score at Visit 3.
Intercurrent Events (ICEs)	ICEs are expected to be rare. Any ICE that does occur will be handled using the treatment policy strategy, i.e., included in the treatment regimen under evaluation.
Population Summary	The proportion of subjects with CGI-I scores of 1 [REDACTED] or 2 [REDACTED] for PH94B will be
	compared to placebo using a comparison of binomial proportions.

7.2.2 Secondary Endpoint and Analysis – CGI-I Scores

The secondary efficacy endpoint in the study is the proportions of CGI-I scores of 1 [REDACTED]
[REDACTED] or 2 [REDACTED] recorded at the end of Visit 3.

The secondary endpoint analysis will compare treatment groups using a normal approximation (Wald) test for the difference between two binomial proportions. The null hypothesis to be tested is that the population proportions of each treatment group are equal. [REDACTED]

[REDACTED]

1000

100

111

10

100

1

100

Page 10

1000

Sponsor: VistaGen Therapeutics, Inc.
Protocol Number: PH94B-CL026

Statistical Analysis Plan

CONFIDENTIAL

Page 25 of 33

[REDACTED]

[REDACTED]

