2.2 SECONDARY EFFICACY OBJECTIVE

The secondary efficacy objective of the Study is the comparison of PH94B-treated subjects with placebo-treated subjects with regard to clinician observed change in subject's response to the anxiety-provoking situation between Visit 2 and Visit 3 as measured by CGI-I.

2.3

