8.2.2.2 Secondary Endpoints

The secondary efficacy endpoint in the Study is the difference between proportions of PH94B- and placebo-treated groups in Clinical Global Impression Scale of Improvement (CGI-I) scores of 1 [REDACTED] or 2 [REDACTED] recorded at the end of Visit 3.

This secondary endpoint will be analyzed using a normal approximation test for the difference between two binomial proportions. The null hypothesis to be tested is that the population proportions are equal.

8.2.2.3 [REDACTED]

[REDACTED]
[REDACTED]
[REDACTED]

[REDACTED]
[REDACTED]
[REDACTED]
[REDACTED]

[REDACTED]
[REDACTED]
[REDACTED]
[REDACTED]

[REDACTED]
[REDACTED]
[REDACTED]
[REDACTED]
[REDACTED]

[REDACTED]
[REDACTED]

[REDACTED]
[REDACTED]

[REDACTED]
[REDACTED]

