1.2 Changes to the Planned Analysis

There are no changes to the planned analysis from the Protocol. Any deviations from the original statistical analysis plan will be described and justified in the final clinical study report.

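### The CGI-I responder test is valid but makes no use of Visit 2 average SUDS, so it may give up a modest amount of precision

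*SAP*

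**What the plan says.** The secondary endpoint is the proportion of subjects with a CGI-I score of 1 or 2 at the end of Visit 3.

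- **Test.** SAP 7.2.2: "The secondary endpoint analysis will compare treatment groups using a normal approximation (Wald) test for the difference between two binomial proportions". Protocol 8.2.2.2 agrees: "This secondary endpoint will be analyzed using a normal approximation test for the difference between two binomial proportions".
- **Estimand.** In SAP 7.2.1 the PH94B proportion is to be "compared to placebo using a comparison of binomial proportions". No covariate is named.
- **Departures.** SAP 1.2: "There are no changes to the planned analysis from the Protocol".
- **Primary model.** SAP 7.1.2: "Treatment group and analysis site will be included as factors and baseline average SUDS score as a covariate".
- **Role in testing.** Under SAP 5.7, CGI-I is tested only after the primary endpoint succeeds. It is the only endpoint in the visible part of that sequence.
- **Missing data.** SAP 5.6 imputes the primary endpoint only.

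The text that follows the null hypothesis in SAP 7.2.2 is blacked out.

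**The concern.** CGI-I is a rating of change. Protocol 2.2 frames it as the observed change in response to the "anxiety-provoking situation between Visit 2 and Visit 3 as measured by CGI-I". The subject's state at Visit 2 is therefore the reference point for the rating, and it may predict who is rated a responder. SUDS is a measure of that state taken before randomisation, and the sponsor already chose it as the covariate for the primary endpoint.

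If Visit 2 SUDS does predict response, a comparison of two raw proportions leaves the explained part of the variance in the error term. The estimate then has a wider interval than the same subjects could provide. What is at stake is some power and some interval width on the gated secondary test. Its validity is not in question.

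**Working it through.** **1. The documents' own figures.** The inputs behind N = 208 are blacked out, so that number cannot be rebuilt. The Phase 2 CGI-I statistic in Protocol 1.2.2 can be:

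- p1 = 34/45 = 0.7556 and p2 = 17/46 = 0.3696, so the difference is 0.3860.
- Wald SE = √(0.7556×0.2444/45 + 0.3696×0.6304/46) = 0.0958.
- Z = 0.3860/0.0958 = 4.03, which matches the reported 4.03.

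The planned test is thus the same type of statistic as in Phase 2.

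**2. Inputs for the comparison.**

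- 104 per arm: Protocol synopsis, statistical methods.
- Two-sided 5%: taken from the 95% intervals in SAP 5.1.
- Placebo rate 37%: Phase 2, Protocol 1.2.2.
- Active rate 56.5%: **assumed**. It puts the raw test near 80% power, where precision matters.
- Correlation of Visit 2 SUDS with CGI-I: **assumed**, with a range shown. It is expressed as ρ, the correlation with a latent normal rating that is cut into responder or not.

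**3. Raw test.** SE = √[(0.565×0.435 + 0.37×0.63)/104] = √(0.4789/104) = 0.0679. Then 0.195/0.0679 = 2.874, and power = Φ(2.874 − 1.960) = 82.0%.

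At the Phase 2 rates, SE = √[(0.756×0.244 + 0.37×0.63)/104] = 0.0634. Then 0.386/0.0634 = 6.09, and power is above 99.9%.

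**4. Effect of adjustment.** The within-arm correlation r with the yes/no response is ρ × φ(z_p)/√(p(1−p)). The multiplier is 0.782 at p = 0.37 and 0.794 at p = 0.565, on average 0.788. The variance ratio (adjusted over raw) should then be about 1 − r², plus a small cost for estimating the slope. Power by formula is Φ(2.874/√ratio − 1.960).

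The proposed estimator was also simulated: a logistic model standardised to the risk difference, with an influence-function SE. Ranges are across separate runs.

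| ρ (assumed) | r | 1 − r² | Simulated variance ratio | Power by formula | Simulated change in power (points) |
|---|---|---|---|---|---|
| 0 | 0 | 1.00 | 1.005 | 81.8% | about -1 to -2 |
| 0.2 | 0.16 | 0.98 | 0.98–0.99 | 82.7% | about 0 |
| 0.3 | 0.24 | 0.94 | 0.95 | 83.9% | about +1 |
| 0.4 | 0.32 | 0.90 | 0.90 | 85.8% | about +2 to +3 |
| 0.5 | 0.39 | 0.84 | 0.85–0.86 | 87.6% (at 0.85) | about +4 to +5 |

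The simulated changes are about a point less favourable than the formula (which gives -0.2 to +5.6). The raw Wald test tends to reject slightly more often in simulation (mostly 82–83%) than its normal approximation predicts (82.0%). That accounts for most of the loss at ρ = 0, where a variance ratio of 1.005 alone would cost only 0.2 points.

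**5. Type I error** at 37% v 37%, across runs: about 4.8–5.9% raw and 4.5–5.7% adjusted. Neither test has a material problem.

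**6. Is ρ up to 0.5 plausible?** If SUDS had equal variance at the two visits and between-visit correlation c, Visit 2 SUDS would correlate with the size of improvement at √((1−c)/2). This is 0.50 at c = 0.5 and 0.32 at c = 0.8. CGI-I would inherit only part of that, so 0.5 is a generous upper end. The value of c is also an assumption.

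**The case against.** The case for leaving the test alone is strong, and most of it stands.

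- The raw test is valid and transparent, and it is the same in both documents. Nothing needs reconciling.
- The benefit rests on a correlation that the documents do not give, and there are reasons to doubt that it is large. CGI-I already rates change from Visit 2, and it is observer-rated while SUDS is self-rated. Protocol 5.2.2 also has a partly blacked-out gate at Visit 2 before subjects go on to Visit 3, so the spread of SUDS among randomised subjects is unknown.
- The 56.5% rate is a chosen scenario. At the Phase 2 rates there is no power to gain.
- At ρ of 0.2 or below the gain is nil, and at zero there is a small loss.

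One counterpoint limits the second item. Under Protocol 3.1 and 5.2.3, the trained observer who records the SUDS scores is the same person at both visits and completes the CGI-I. The rater has heard the SUDS values, so some correlation is plausible.

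A reader might infer that chance imbalance in Visit 2 anxiety biases the responder difference. It does not: under randomisation the standard error of the raw difference already covers such imbalance. A reader might also infer that no adjusted CGI-I analysis is planned. That cannot be said, because the blacked-out text in SAP 7.2.2 could hold a supportive one. What is visible is that the named test is unadjusted.

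**Conclusion.** The point holds as an optional improvement in efficiency. The visible CGI-I test is unadjusted and leaves unused a covariate measured before randomisation that the primary model already uses.

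Under the stated assumptions (104 per arm, 37% v 56.5%, ρ from 0 to 0.5), adjustment would save between nothing and about 15% of the variance and move power by about -1 to +5 points. If the Phase 2 rates recur, the only benefit is a narrower interval. A 15% variance saving would shorten it by about 8%, since √0.85 = 0.92.

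The documents do not support a claim that the test is wrong, or that the trial is underpowered for CGI-I. No power target for this endpoint is visible, and the raw test reaches 80% power at an active rate of about 56% against 37%. Confidence in the size of the gain is low, because the correlation is unknown.

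**What to change.** Keep the estimand: the difference in proportions with CGI-I 1 or 2. Before database lock and unblinding, pre-specify in SAP 7.2.2:

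1. A logistic model with treatment and Visit 2 average SUDS. Add analysis site, as grouped for the primary model, if it can be estimated. With 208 subjects over up to about 18 centres (208/18 ≈ 11.6 each), the SAP should say that site is dropped if it cannot.
2. Standardisation of the model to a marginal risk difference, with a robust or influence-function SE. A conditional odds ratio should not replace it, because that would change the summary measure.
3. Averaging over randomised subjects with an observed CGI-I. Averaging over every randomised subject would supply predictions for missing ratings and conflict with the no-imputation rule in SAP 5.6.
4. The raw Wald difference as a supportive result.

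Because the Protocol names the raw test, record the change in SAP 1.2, which now declares none. A lighter option keeps the Wald test as confirmatory and adds the adjusted estimate as supportive. That brings the narrower interval but no gain for the gated test.

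Cost: SAP wording and a standard procedure, with no new data. The analysis becomes slightly more complex, and about 1 point of power is lost if Visit 2 SUDS does not predict CGI-I.
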